3.2.3. Other Efficacy Endpoints

- Response based on the IGA for clear (0) at all scheduled time points;
- Response based on a $\geq 50\%$, $\geq 90\%$ and $=100\%$ improvement in the EASI total score (EASI-50, EASI-90 and EASI-100) at all scheduled time points;
- Percent change from baseline at all scheduled time points in the EASI total score;
- Change from baseline in %BSA (from EASI) affected at all scheduled time points;
- Proportion of patients with %BSA (from EASI) $< 5\%$ at all scheduled time points;
- Response based on a $\geq 50\%$ and $\geq 75\%$ improvement in SCORAD (SCORAD50, SCORAD75) from baseline at all scheduled time points. A detailed description of the derivation of the SCORAD score is provided in [Appendix 7](#);
- Percent change from baseline at all scheduled time points in the SCORAD total score;
- Change from baseline at all scheduled time points in SCORAD subjective VAS assessments of sleep loss.

CCI [REDACTED]
[REDACTED]
[REDACTED]
[REDACTED]
[REDACTED]
[REDACTED]
[REDACTED]
[REDACTED]
[REDACTED]
[REDACTED]
[REDACTED]
[REDACTED]
[REDACTED]
[REDACTED]

C
C
I

[REDACTED]

[REDACTED]

[REDACTED]

[REDACTED]

[REDACTED]

[REDACTED]

[REDACTED]

[REDACTED]

[REDACTED]

[REDACTED]

[REDACTED]

[REDACTED]

[REDACTED]

[REDACTED]

[REDACTED]

[REDACTED]

[REDACTED]

[REDACTED]

[REDACTED]

[REDACTED]

3.3.3. PK Endpoints

The PK endpoints and the analysis methods for these endpoints are described in a separate analysis plan.

3.4. Baseline Variables

In general, for all analyses, baseline will be defined based on observations collected prior to first dose. Baseline values for demographics, medical and other history, atopic dermatitis history will be based on measures collected at Visit 1 / Screening visit. Study Day 1 is defined as the day the subject receives first dose of study drug. For purposes of all other analyses including analyses for change from baseline, the baseline value will be defined as measured on Day 1 (before time of first dose, if time is available). If a value is missing on Day 1, then the last available observation before Day 1 will be used. For the PSAAD score, baseline will be defined as the average of all values recorded from Day -6 until Visit 2 / Day 1. For analysis purposes, randomization strata information will be taken from the Case Report Form (CRF). Baseline disease severity will be defined using the IGA score at baseline. For endpoints which are not time sensitive, measurements taken on Day 1 after the first dose may be used as baseline observations.

3.5. Safety Endpoints

Safety will be assessed by the spontaneous reporting of AEs, physical examinations, and clinical laboratory results in all subjects who receive at least one dose of the investigational product. Unscheduled safety assessments may be performed at any time during the study to assess any perceived safety concerns. Endpoints will be assessed as,

- Incidence of treatment emergent adverse events.
- Incidence of SAEs and AEs leading to discontinuation.
- Incidence of clinical abnormalities and change from baseline in selected clinical laboratory values, ECG measurements, and vital signs.

The safety endpoints will be defined in accordance with Pfizer Data Standards.

3.5.1. Adverse Events

An adverse event will be considered a Treatment-Emergent Adverse Event (TEAE) if the event started during the effective duration of treatment. All events that start on or after the first dosing day and time / start time, if collected, but before the last dose plus the lag time (28 days) will be flagged as TEAEs. The algorithm will not consider any events that started prior to the first dose date.

A 3-tier approach will be used to summarize AEs. Under this approach, AEs are classified into one of 3 tiers. Different analyses will be performed for different tiers (See [Section 6.10.1](#)).

Tier-1 events: These are pre-specified events of clinical importance and are maintained in a list in the product's Safety Review Plan. Herpes zoster and serious infections have been identified as Tier-1 events. No other Tier-1 events have been identified so far and the study team will continue monitoring all safety events.

Tier-2 events: These are events that are not Tier-1 but are "common". A MedDRA Preferred Term (PT) is defined as a Tier-2 event if there are at least 4 subjects with an event in any treatment group.

Tier-3 events: These are events that are neither Tier-1 nor Tier-2 events.

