6.1. Visit 1, Screening

Subjects will be screened (Visit 1) within 28 days prior to administration of the investigational product to confirm that they meet the subject selection criteria for the study. The investigator (or an appropriate delegate at the investigator site) will obtain informed consent from each subject, or parent(s)/legal guardian (and assent from the subject, as appropriate), in accordance with the procedures described in the [Subject Information and Consent](#) in [Section 12.3](#).

If the Mantoux PPD tuberculin skin test is given, the subject must return between 48-72 hours post-injection for induration evaluation.

Screening laboratory tests with abnormal results may be repeated once to confirm abnormal results; the last value will be used to determine eligibility. If results return to normal within the 4-week screening period, the subject may enter the study.

The following procedures will be completed:

- Obtain written informed consent; for subjects aged less than the legal age of majority (legal adulthood) in the subject's country, obtain written informed consent from parent(s)/legal guardian, and informed assent from the patient (if age appropriate according to local regulations);
- Register subject using the IRT system;
- Collect demography;
- Administer C-SSRS, SBQ-R and PHQ-8. Subjects meeting any of the criteria specified in Exclusion Criterion 2 as described in [Section 4.2](#) on the C-SSRS, SBQ-R and PHQ-8 should be excluded from participation; it is recommended the subject's primary care physician (PCP) should be informed, and the subject referred to a mental health professional, either by the PCP or the investigator according to their usual practice;
- Complete medical history, including history of alcohol and tobacco use. Smoking status and average weekly alcohol consumption (units/week) will also be collected, where a unit contains 12 g of pure alcohol, an amount equivalent to that contained in

5 oz/150 ml (a glass) of wine, 12 oz/360 ml of beer, or 1.5 oz/45 ml of 90 proof (45% alcohol by volume) of spirits;

- Complete AD disease history includes collection of details of AD: AD diagnosis and duration, the use of topical treatments, systemic treatments and other treatments for AD;
- Obtain complete medication history of all prescription or nonprescription drugs, and dietary and herbal supplements taken within 28 days prior to the planned first dose, except as noted below:

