- For Japan only: In addition to HBsAg and HBcAb, HBsAb testing will be performed at Screening for all subjects rather than as a reflex test. Subjects with negative results for HBsAg, HBcAb and HBsAb may be eligible. Subjects who are HBsAg negative, HBcAb negative and HBsAb positive and provide documentation of prior HBV vaccination may be eligible and will not require HBV DNA monitoring during the study. Subjects who are HBsAg negative, HBcAb negative and HBsAb positive without documentation of prior HBV vaccination AND subjects who are HBsAg negative, HBcAb positive, and HBsAb positive at screening will have reflex testing for HBV DNA. Subjects who are HBV DNA negative or below LLQ may be randomized but will have HBV DNA repeated at Week 12 or early termination.
- QuantiFERON[®] – TB Gold test or locally analyzed T-SPOT[®].TB test (Japan only) (unless performed within 12 weeks of Day 1). If Mantoux PPD tuberculin skin test is required to be performed instead, per [Section 7.3.4](#), the subject must return between 48-72 hours post-injection for evaluation of induration (see [Section 7.3.4](#) for further details on TB testing);
- Conduct clinical evaluations including IGA, SCORAD, EASI and BSA (calculated in the EASI);
- Assess need for contraception and adherence to applicable lifestyle requirements ([Section 4.4](#)). Establish willingness and ability to comply with lifestyle requirements going forward in the study;
- Review Inclusion and Exclusion criteria for subject eligibility;
- Assess for occurrence of Adverse Events: The adverse event and SAE reporting period starts with the signing of the informed consent document;
- If the subject is eligible for continued participation, provide subject with emergency contact card.

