8.1.4. Time Period for Collecting AE/SAE Information

The time period for actively eliciting and collecting AEs and SAEs (“active collection period”) for each subject begins from the time the subject/parent(s)/legal guardian, if applicable, provides informed consent, which is obtained before the subject’s participation in the study (ie, before undergoing any study-related procedure and/or receiving investigational product), through and including a minimum of 28 calendar days; except as indicated below after the last administration of the investigational product.

For subjects who are screen failures, the active collection period ends when screen failure status is determined.

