8.3. Severity Assessment

If required on the AE page of the CRF, the investigator will use the adjectives MILD, MODERATE, or SEVERE to describe the maximum intensity of the AE. For purposes of consistency, these intensity grades are defined as follows:	
MILD	Does not interfere with subject's usual function.
MODERATE	Interferes to some extent with subject's usual function.
SEVERE	Interferes significantly with subject's usual function.

Note the distinction between the severity and the seriousness of an AE. A severe event is not necessarily an SAE. For example, a headache may be severe (interferes significantly with the subject's usual function) but would not be classified as serious unless it met one of the criteria for SAEs, listed above.

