6.10.1. Adverse Events

The safety data will be summarized in accordance with CaPS. All safety data will be summarized descriptively through appropriate data tabulations, descriptive statistics, categorical summaries, and graphical presentations. Safety endpoints for the study include:

- Treatment-emergent AEs and SAEs;
- Withdrawals from active treatment due to AEs;
- Serious infections, defined as any infection (viral, bacterial, and fungal) requiring hospitalization or parenteral antimicrobials.

Treatment-emergent AEs will also be analyzed using a 3-tier approach. Risk differences between the active treatments and placebo will be used to summarize the results.

For Tier-1 events, point estimates, 95% confidence intervals and p-values will be presented graphically comparing each active dose group with placebo. No multiplicity adjustments will be made. For Tier-2 events, only point estimates and 95% confidence intervals will be presented graphically (see [Section 5.2.6](#)). Tier-3 events will be summarized as part of the overall AE summaries, AEs will be displayed by MedDRA system organ class (SOC).

It should be recognized that most studies are not designed to reliably demonstrate a causal relationship between the use of a pharmaceutical product and an adverse event or a group of

adverse events. Except for select events in unique situations, studies do not employ formal adjudication procedures for the purpose of event classification. As such, safety analysis is generally considered as an exploratory analysis and its purpose is to generate hypotheses for further investigation. The 3-tier approach facilitates this exploratory analysis.

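### Treatment emergence is judged on start date alone, so a screening-onset adverse event that worsens on study drug under its original record is left out of TEAE incidence and the tiered comparisons

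*SAP*

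**What the plan says.** SAP 3.5.1 counts an event as treatment-emergent "if the event started during the effective duration of treatment". The window opens at the first dose, and events starting "before the last dose plus the lag time (28 days) will be flagged as TEAEs". The section then closes off everything earlier: "The algorithm will not consider any events that started prior to the first dose date". It says nothing about an event already present at the first dose that later worsens or becomes serious. The protocol uses the term treatment-emergent but does not define it, so nothing there overrides the SAP.

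Collection starts well before dosing. Protocol 8.1.4 says the active collection period "begins from the time the subject/parent(s)/legal guardian, if applicable, provides informed consent", and Protocol 6.1 agrees: "The adverse event and SAE reporting period starts with the signing of the informed consent document". The gap can be four weeks: "Subjects will be screened (Visit 1) within 28 days prior to administration of the investigational product".

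Protocol 8.3 grades each event once, using a mild, moderate or severe label "to describe the maximum intensity of the AE".

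The flag feeds the main safety comparison. TEAE incidence is a safety endpoint in SAP 3.5, and SAP 6.10.1 states: "Treatment-emergent AEs will also be analyzed using a 3-tier approach". SAP 3.5.1 names herpes zoster and serious infections as the Tier-1 events.

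**The concern.** For a JAK1 inhibitor, one safety question is whether an infection or other condition already present at the first dose progresses more often on drug. Randomisation should balance events that began in screening, but progression after dosing need not be balanced. A flag based only on the start date treats a screening event that stayed mild and one that led to hospital admission on drug in the same way: neither counts.

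Screening is also a period in which events are likely, because existing atopic dermatitis treatment is washed out then and Protocol 8.2.1 lists worsening of the underlying disease as an example of an adverse event. The protocol treats worsening as meaningful elsewhere: under 8.2.4, an admission for a pre-existing condition escapes being an SAE only if no new event and no worsening is involved. At stake is the completeness of the between-arm TEAE and tiered comparisons, which are the only adverse-event comparisons for which the SAP specifies risk differences and confidence intervals.

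**Working it through.** The plan gives no figure that depends on this rule, so there is nothing to reproduce. The check applies the rule to test cases and then follows the result into the outputs.

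**Step 1: the rule.** An event is a TEAE if first dose ≤ start < last dose + 28 days. With dosing on Days 1 to 85 (Schedule of Activities), this is Day 1 ≤ start < Day 113, since 85 + 28 = 113. The comparison rule also counts a pre-dose event whose worsening date falls in the same window.

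| Case | SAP 3.5.1 as written | Onset or worsening |
|---|---|---|
| Onset Day -10, severe or serious on Day 20, same record | not TEAE | TEAE |
| Onset Day -10, no worsening | not TEAE | not TEAE |
| Onset Day -10, worsening entered as a new record on Day 20 | TEAE | TEAE |
| Onset Day 20 | TEAE | TEAE |
| Onset Day 112 | TEAE | TEAE |
| Onset Day 113 | not TEAE | not TEAE |

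The two rules differ only in the first row.

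**Step 2: can the first row occur?** Collection from consent allows onset up to 28 days before dosing. Protocol 8.1.4.1 and 8.1.4.2 provide for follow-up of an event until it resolves or stabilises, and 8.3 gives it one maximum grade. No section tells sites to close the record and open another when the grade rises. On the plain reading, a mild event from Day -10 that becomes severe on Day 20 is one record, graded severe and dated Day -10.

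**Step 3: which outputs lose it?** TEAE incidence (SAP 3.5) and the tiered risk differences (SAP 5.2.6 and 6.10.1) depend on the flag. The separate SAE and discontinuation endpoints in SAP 3.5, and the all-AE, SAE and withdrawal summaries in SAP 6.10, are not worded as limited to TEAEs.

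**Step 4: what one subject is worth.** With planned arms of 150, 150 and 75:

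- active arm: 1/150 = 0.67 percentage points;
- placebo arm: 1/75 = 1.33 percentage points.

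Tier-2 status needs at least 4 subjects with a preferred term in any group. As an illustration with assumed counts, suppose an active arm has 3 flagged subjects and 1 whose pre-dose event worsened. The arm then shows 3/150 = 2.0% instead of 4/150 = 2.7%, and the term misses the threshold in that arm.

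**The case against.** Several counter-arguments have force.

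- **New records.** A reader might infer that a screening event can never become treatment-emergent. The documents do not support that. Sites record events since the last visit at each visit, and a worsening entered as a new event with an on-treatment start date is flagged. What remains is that neither document asks for this, so practice may vary between sites.
- **Other outputs.** A reader might also infer that a drug effect on an existing infection could not show at all. That goes too far. A hospital admission would be reported as an SAE and appear in the summaries named in Step 3. SAP 6.10.1 lists serious infections as a safety endpoint in its own right. The E-DMC monitors safety, and blinded committees adjudicate opportunistic and other selected infections (Protocol 9.5 and 9.6). The loss is confined to TEAE incidence and the tiers.
- **Eligibility.** Exclusion 12 in Protocol 4.2 removes clinically significant systemic infections within 6 months of Day 1, skin infections needing systemic treatment within 2 weeks and superficial ones within 1 week. This takes out many of the infections of most concern, but not an infection judged minor on Day 1 that progresses later.
- **Deliberate choice.** The SAP change log says the definition was updated to align with an external standard, SAP 6.10.1 calls safety analysis generally exploratory, and the rule is the same in all arms. This explains the rule's origin. It gives no reason for leaving out worsening.
- **Frequency.** It is tempting to attach a rate. Assuming 5 to 15% of subjects have a screening-onset event and 5 to 10% of those worsen gives 0.05 × 0.05 = 0.25% to 0.15 × 0.10 = 1.5% of subjects. Neither input is in the documents, and the product covers all event terms, of which Tier-1 events would be an unknown part. It is not evidence of loss.

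**Conclusion.** The concern holds in a limited form. Followed as written, SAP 3.5.1 omits from TEAE incidence and the tiered risk differences any screening-onset event that stays on its original record and becomes serious or worsens on study drug. That includes the Tier-1 serious-infection comparison. This is a stated rule that gives an incomplete count; it is not a contradiction between sections, and it does not affect efficacy.

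The number affected is probably small and cannot be estimated from the documents. The per-subject figures in Step 4 show only how far one omitted case would move a rate. The conclusion rests on two assumptions: that at least some sites keep worsening on the original record, and that no CRF instruction outside these documents says otherwise.

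**What to change.** In SAP 3.5.1, also flag as treatment-emergent any event with onset before the first dose that meets a seriousness criterion, by its SAE date, on or after the first dose and before last dose plus 28 days. If the standard flag must stay, list these events by arm in a supplementary table and include them in the Tier-1 serious-infection comparison as a sensitivity analysis.

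Apply the same rule to increases in severity where a dated worsening or a separate record exists. Add a CRF completion note that post-dose worsening of a screening event is entered as a new record dated at the worsening. The SAP sentence alone is not enough for severity, because a single maximum grade carries no date.

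The cost is a small departure from the sponsor's standard algorithm, slightly higher TEAE counts and a site instruction. SAP 5.3.1 describes data already lost at Week 2 and later, so the trial was under way when this SAP version was written. Severity dating will therefore stay incomplete for records already entered unless they are queried.

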3.5.2. Laboratory Data

Below is a list of hematology and serum chemistry test parameters.

- Hematology: hemoglobin, hematocrit, red blood cell count, reticulocyte count, platelet count, white blood cell count with differential, total neutrophils, eosinophils, monocytes, basophils, lymphocytes, coagulation panel.
- Serum chemistry: blood urea nitrogen, creatinine, creatine phosphokinase, glucose, sodium, potassium, chloride, calcium, total bicarbonate, aspartate aminotransferase,

alanine aminotransferase, gamma-glutamyl transferase, bilirubin, alkaline phosphatase, lactate dehydrogenase, uric acid, albumin, total protein, total cholesterol, low-density lipoprotein (LDL), high-density lipoprotein (HDL), triglycerides.

3.5.3. Vital Signs, including Height and Weight

Vital sign measurements are oral or tympanic temperature, respiratory rate, pulse rate, and blood pressures.

Height and weight are collected at pre- and post-treatment.

3.5.4. Physical Examinations

Complete physical examinations consist of assessments of general appearance; skin; head, eyes, ears, nose and throat; mouth, heart; lungs; breast (optional); abdomen; external genitalia (optional); extremities; neurologic function; and lymph nodes.

4. ANALYSIS SETS

Data for all subjects will be assessed to determine if subjects meet the criteria for inclusion in each analysis population described below prior to unblinding and releasing the database and classifications will be documented per standard operating procedures.

4.1. Full Analysis Set

The Full Analysis Set (FAS) is defined as all subjects who have been randomized and who have received at least one dose of treatment. Subject is assigned to the randomized treatment group regardless of actual treatment received. Analyses for endpoints that are defined based on a threshold of change from baseline (e.g. NRS4) will also require the baseline value to meet that threshold (e.g. for NRS4, the baseline value needs to be ≥ 4).

It is expected that the FAS as defined here will be identical to an ITT analysis set (randomized and dispensed study medication) because the first dose is administered in-clinic. The number of subjects randomized and dispensed study medication but did not receive treatment will be reported.

4.2. Per Protocol Analysis Set

The Per Protocol Analysis Set (PPAS) is defined as a subset of FAS who had no major protocol violations. The subjects excluded from the PPAS will be determined and documented before the study is unblinded. The primary and key secondary endpoints will be analyzed for the PPAS. This set will include subjects who:

- Were eligible for the study by way of meeting key inclusion criteria and none of the key exclusion criteria.
- Had valid and non-missing baseline efficacy data (IGA and EASI score). Had actual, observed IGA and EASI scores at Visit 8 / Week 12.

- Did not take a protocol-prohibited medication for the primary diagnosis prior to completion of the study dosing period (Visit 8 / Week 12).
- Took the correct randomized treatment for at least 80% and at most 120% of the assigned amount until completion of the study dosing period (Visit 8 / Week 12).
- Had no other major protocol violations that is likely to affect materially the efficacy responses of the subject as determined by the clinical team prior to database lock.

These items will either be assessed by programmed checks of the data or be determined by clinical review prior to unblinding of study treatment.

